The purpose of this study is to prospectively compare preoperative (neoadjuvant) SRS/SRT to postoperative (adjuvant) SRS/SRT in patients undergoing surgical resection for brain metastases.

Hypothesis, Objectives, and Outcomes

We hypothesize that neoadjuvant SRS/SRT prior to surgical resection of brain metastases will result in improved freedom from Central Nervous System (CNS) events when compared to adjuvant SRS/SRT after surgical resection.

Primary Objectives

- Our primary objectives are: (1) to determine the *Time to a Central Nervous System* (*CNS*) *Composite Event* (*CE*) in subjects who receive either neoadjuvant (preoperative) SRS/SRT or adjuvant (post-operative) SRS/SRT for their brain metastases, and (2) to compare the two treatment arms for evidence of improved Time to a CNS CE among subjects who received neoadjuvant SRS/SRT.
 - A CNS CE will consist of one of the following three events: Local Recurrence (LR) of the treated lesions, symptomatic radiation necrosis (SRN) to the treated lesions, or development of leptomeningeal disease (LMD). See below for detailed definitions of LR, SRN, and LMD.
 - Time to a CNS CE, the primary outcome, will be measured as the time from the date of randomization to the date of a documented LR, SRN, or LMD, whichever occurs first.
 - Death before occurrence of a CNS CE will be treated as a competing risk. Study participants who are alive and have yet to experience a CNS CE at their last evaluation will be right-censored for Time to CNS CE on the date of their last evaluation.

Secondary Objectives related to the Primary Objective. Some of our secondary objectives include (a) determining in each study subject the *secondary outcomes* listed below, and (b) comparing the treatment arms for evidence of improvements in these secondary outcomes.

- Index lesion local recurrence (ILLR), a component of CNS CE, will be defined as the development of new nodular contrast enhancement in the surgical bed compared with the immediate postoperative MRI.
- Non-index lesion LR, also a component of CNS CE, will be defined as an increase of more than 25% in the size of any treated non-resected brain lesion.

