- Time to subsequent brain treatment, including whole-brain radiotherapy (WBRT), will be measured as the time from the date when the assigned treatment is successfully completed to the date when the WBRT or other subsequent treatment is initiated.
- Radiation/Surgery toxicity
 - o The rate of symptomatic (≥grade 2) radiation/surgery toxicity

 Incidence of adverse events as graded by the National Cancer Institute (NCI) Common Terminology Criteria for Adverse Events (CTCAE) version 5.0

Study Design and Procedures

Design: This pilot study is a randomized, open-label, 2-arm active-controlled phase II clinical trial conducted at a single study site (UAMS) located in central Arkansas. Prospective enrollees will be screened based on the inclusion/exclusion criteria listed below in the *Study Population* section. Study-eligible candidates who agree to participate will be assigned by randomization to one of the 2 treatment arms shown in the table below:

Treatment Arm	Intervention/treatment
Experimental: Arm I (pre-operative SRS/SRT)	Radiation: Stereotactic Radiosurgery Undergo SRS/SRT Other Names:
Patients undergo SRS or SRT within 15 days of randomization followed by surgery within 15 days of radiation completion. Patients may undergo	Stereotactic External Beam Irradiation
	 stereotactic external-beam radiation therapy
additional SRS or SRT if disease returns after treatment.	stereotactic radiation therapy
	Stereotactic Radiotherapy
	 stereotaxic radiation therapy
	 stereotaxic radiosurgery
Active Comparator: Arm II (post- operative SRS/SRT) Patients undergo surgery within 15 days of randomization followed by standard-of-care SRS or SRT within 30	Undergo SRS/SRT Other Names: • Stereotactic External Beam Irradiation
	 stereotactic external-beam radiation therapy
days of surgery. Patients may undergo additional SRS or SRT if disease	stereotactic radiation therapy
returns after treatment.	Stereotactic Radiotherapy
	 stereotaxic radiation therapy
	stereotaxic radiosurgery

The dose, volume and fractionation of radiotherapy will be at the discretion of the radiation oncologist at the time of SRS/SRT depending on the size, location, and proximity to critical structures. Before treatment commences, each study participant will be stratified according to two stratification factors:

- Size of Index Lesion (<3 cm versus ≥3 cm)
- Number of Brain Metastases (4 or fewer versus 5 or more)

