These stratification factors will be used during the randomization procedure to assure that the treatment arms will be well-balanced with respect to index-lesion size and brainmetastasis number.

On-study Plan: After first signing the IRB-approved Informed Consent form, and after then being stratified according to size of index lesion and number of brain metastases, study participants will be registered and assigned a study number by a clinical research associate (CRA) or Study Coordinator.

Randomization and Treatment Allocation: After the study participant's eligibility has been confirmed, and after the participant has been stratified (see above) and registered in the Research Participant Registration System (RPRS), the study coordinator will do two things. First, the study coordinator will use the RPRS to assign the participant to one of the four possible strata defined by the stratification factors. Then the study coordinator will use the RPRS to randomize the participant in a 1:1 allocation ratio to either Arm I (pre-operative SRS/SRT) or Arm II (post-operative SRS/SRT). The randomizations will be balanced 1:1 on treatment arms within each stratum by using a permuted-blocks approach. Study participants will receive either pre-operative or post-operative SRS/SRT depending on the study arm to which they are randomized. Accordingly the two study arms will follow the treatment schedules shown in the table.

Sample Collection: The extent (gross total or subtotal resection) and technique for surgery (en bloc or piecemeal) will be determined by the neurosurgeon. The pathological specimen will be analyzed and stored by the Department Pathology per standard operating procedure for resected brain tumor specimens.

Follow-up: After completion of radiotherapy and surgery, study subjects will be followed by Brain MRI every 2-3 months for the first year and then every 4-6 months indefinitely (in accordance with National Comprehensive Cancer Network [NCCN] guidelines). Imaging and follow-up can be done sooner than these specified times if clinically indicated. MRI's will be included in study results up to 18 months.

Study Population

Ages Eligible for Study: Sexes Eligible for Study: Accepts Healthy Volunteers: Estimated Enrollment 18 Years and older (Adult, Older Adult)AllNo104 (we anticipate consenting 120 in order to reach this goal)

Inclusion Criteria

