Data Safety Monitoring Plan: The study will be monitored by the investigators to ensure that the rights and well-being of human subjects are protected, that the data are accurate, complete and verifiable from source documents and that the trial is conducted in compliance with currently approved protocol/amendments. The PI and sub-Investigators will review study conduct on an ongoing basis. The PI will assure that all protocol deviations, AEs, and SAEs are reported to the IRB according to the applicable regulatory requirements.

Specimen Handling and Storage

Tumor specimens will be collected from surgical resection and stored by the Department of Pathology and kept as part of standard of care. No samples will be collected specifically for use in this study at this time.

Data Analysis

Statistical analysis plan

Patient characteristics will include patient demographics, disease characteristics of the primary tumor, and relevant characteristics (number, location, size, etc.) of the brain metastases being treated. Patient characteristics will be summarized by treatment arm with medians, quartiles, and ranges for numeric characteristics, or with numbers and percentages for category characteristics. Each characteristic then will be assessed for imbalance between treatment arms with Wilcoxon's rank-sum test for numeric characteristics. The imbalance assessments will consist of 2-sided tests that employ the standard α =0.05 significance level.

Time to a CNS CE, the primary outcome, will be visualized with Cumulative Incidence (CI) curves computed using Kaplan-Meier methodology, summarized by treatment group as CI proportions at 6, 12, and 18 months, and compared for difference using the Fine and Gray model for equality of CI functions when death before a CNS CE is treated as a competing risk. Times to each of the individual CNS events (LR, SRN, LMD, DiBF, and WBRT) will be analyzed the same way, except that each Fine and Gray model will have the competing risk be death before the individual event being analyzed. Overall survival will be visualized using standard Kaplan-Meier curves and compared for differences via the log-rank test. Because this is a pilot study, all time-to-event outcomes will be compared for evidence of improvement on the pre-operative SRS/SRT arm using 1-sided tests that employ an α =0.10 significance level.

Sample size, power, and study duration

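### Routine MRI is timed from treatment completion but incidence is reported at 6, 12 and 18 months from randomization, so at the longest permitted intervals no routine scan falls between about months 13 and 19

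*Combined protocol and SAP*

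**What the plan says.** **Outcome clock.** Under Primary Objectives, time to a CNS composite event is "measured as the time from the date of randomization to the date of a documented LR, SRN, or LMD, whichever occurs first". Times to LR, LMD, SRN and distant in-brain failure have the same origin. The Statistical analysis plan has the primary outcome "summarized by treatment group as CI proportions at 6, 12, and 18 months".

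**Scan clock.** Under Follow-up, routine imaging begins only when both treatments are finished: "After completion of radiotherapy and surgery, study subjects will be followed by Brain MRI every 2-3 months for the first year and then every 4-6" (the last interval is also in months). Earlier imaging is allowed when clinically indicated. MRIs enter the study results for 18 months, but the paragraph does not say from which date.

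**Treatment windows.** The treatment-arm table says for Arm I: "Patients undergo SRS or SRT within 15 days of randomization followed by surgery within 15 days of radiation completion". In Arm II, surgery is within 15 days of randomization, "followed by standard-of-care SRS or SRT within 30" days of surgery.

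**The concern.** LR is defined by enhancement or growth on MRI. Radiation necrosis is suspected and confirmed on imaging, and LMD is diagnosed by imaging or spinal fluid. For an event without symptoms, the recorded date is therefore largely the date of the scan that showed it. If no routine scan falls shortly before a landmark, silent events since the last scan are not counted at that landmark. They are dated to the next scan, or never recorded.

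Nothing in the plan ties scans to months 6, 12 and 18 from randomization. The scan calendar depends on when treatment ended and on which interval in each permitted range was chosen. What is at stake is the meaning of the landmark proportions: an 18-month figure could in practice describe routine imaging to about month 13, and a 6-month figure imaging to about month 4.

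**Working it through.** The plan states no scan date from randomization and no landmark incidence, so it has no figure of its own to reproduce.

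**Inputs from the documents**
- Latest completion (treatment-arm table): Arm I 15 + 15 = 30 days; Arm II 15 + 30 = 45 days. Dividing by 30.44 gives 1.0 and 1.5 months. A multi-day SRT course could add a few days.
- Scan intervals (Follow-up): 2-3 months in the first year, then 4-6 months.
- Rates (Sample size, power, and study duration): composite events 25% per year in Arm II and 12.5% in Arm I; competing deaths 32% per year in both.

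**Assumptions**
- The annual rates are constant hazards.
- The first year is the year after completion.
- Events are found only on routine scans.

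**Step 1: routine scan dates**, in months from randomization, with full treatment windows:

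| Intervals | Arm I | Arm II |
|---|---|---|
| 3 then 6 months | 4, 7, 10, 13, 19 | 4.5, 7.5, 10.5, 13.5, 19.5 |
| 2 then 4 months | 3, 5, 7, 9, 11, 13, 17 | 3.5, 5.5, 7.5, 9.5, 11.5, 13.5, 17.5 |

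At the longest intervals, the last routine scan before months 6, 12 and 18 is at 4, 10 and 13 in Arm I and at 4.5, 10.5 and 13.5 in Arm II. With no treatment delay at all, the late gap would still run from month 12 to month 18.

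**Step 2: incidence at the landmark and at the last scan before it.** With event hazard λ, death hazard μ = 0.32 and t in years:

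CIF(t) = λ/(λ+μ) × [1 − exp(−(λ+μ)t)]

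Arm II (λ = 0.25, λ/(λ+μ) = 0.4386):
- Month 18: 0.4386 × (1 − 0.4253) = 25.2%.
- Month 13.5: 0.4386 × (1 − 0.5266) = 20.8%.

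Arm I (λ = 0.125, λ/(λ+μ) = 0.2809):
- Month 18: 0.2809 × (1 − 0.5130) = 13.7%.
- Month 13: 0.2809 × (1 − 0.6175) = 10.7%.

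The other landmarks follow in the same way:

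| Landmark | Arm | At landmark | At last routine scan | Relative shortfall |
|---|---|---|---|---|
| 6 | I | 5.6% | 3.9% (month 4) | 30.9% |
| 6 | II | 10.9% | 8.4% (month 4.5) | 22.4% |
| 12 | I | 10.1% | 8.7% (month 10) | 13.7% |
| 12 | II | 19.1% | 17.2% (month 10.5) | 9.6% |
| 18 | I | 13.7% | 10.7% (month 13) | 21.5% |
| 18 | II | 25.2% | 20.8% (month 13.5) | 17.6% |

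An event first seen at month 19 or 19.5 is dated after month 18. The 18-month shortfall is therefore the same whether or not that scan enters the results.

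**Step 3: sensitivity.** With 2- then 4-monthly scans, the 18-month figures read 24.8% instead of 25.2% (Arm II, month 17.5) and 13.1% instead of 13.7% (Arm I, month 17). If the first year is counted from randomization, the longest-interval Arm I scans fall at 4, 7, 10 and 16, and its 18-month figure reads 12.6% instead of 13.7%; the 6- and 12-month rows do not change.

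**Step 4: the shift between arms.** Give both arms the same hazard (0.25) and the Step 1 dates for the longest intervals. Arm I then reads 7.6% against 8.4% in Arm II at 6 months, 16.6% against 17.2% at 12, and 20.2% against 20.8% at 18. The later Arm II scan captures slightly more events before each landmark, although each Arm II event is dated later. In a simulation with equal hazards and completion at day 30 versus day 45, the observed Arm II/Arm I rate ratio was about 1.00-1.03.

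**The case against.** The strongest reply is that this is ordinary imaging follow-up. The intervals follow stated national guidance, both arms have the same schedule, and periodic imaging blurs event dates in any such trial. The figures above need every patient to use the full windows and the longest intervals, with nothing found off schedule. Clinically indicated scans are allowed, symptomatic necrosis by definition brings symptoms, and LMD can be found in spinal fluid, so some events will not wait for a routine scan. All of this stands, and it makes the figures a worst case for timing. One feature works the other way: the formula counts silent events in patients who die before the next scan, and these might never be recorded.

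A reader might infer more: that Arm II scans necessarily come later and so bias the comparison against Arm I. The documents do not support this. The windows are upper limits, so completion dates can coincide or reverse, and the permitted shift is about 15 days at most. Its direction is not clear either. In the worst case the absolute difference at 6 months shrinks (10.9 − 5.6 = 5.3 points to 8.4 − 3.9 = about 4.6 before rounding), while the Arm I/Arm II ratio moves in favour of Arm I (0.515 to 0.459). A reader might also infer that unblinded staff would scan one arm more often. The intervals leave room for that, but nothing in the documents indicates it.

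**Conclusion.** The point holds for the landmark estimates. Scan and outcome clocks have different origins, no scan is tied to a landmark, and the 18-month MRI limit has no stated origin. At the longest intervals with full windows, and with the first year counted from completion, neither arm has a routine scan between about months 13 and 19. The planned proportions could then understate incidence by about 18-31% in relative terms at 6 and 18 months and about 10-14% at 12 months. Shorter intervals, earlier completion and symptom-triggered imaging all reduce this.

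The late gap comes mainly from the permitted 6-month interval and affects both arms almost equally. The shift between arms has little effect on the overall comparison and no clear direction, so the case for change rests on the landmarks alone. It is a cheap improvement worth making, and it does not invalidate the primary test.

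**What to change.** In the Follow-up paragraph:
- Count study MRIs from randomization, with the same target months and windows in both arms, within the existing 2-3 and 4-6 month intervals.
- Place a study MRI at or just before months 6, 12 and 18. Months 3, 6, 9, 12 and 18 would satisfy this, with windows that close at the landmark.
- State that the 18-month limit on MRIs runs from randomization.
- Keep clinically indicated scans as they are.

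The cost is protocol wording and scheduling windows, with roughly the same number of scans. A small downside is that the first follow-up scan may come slightly sooner after treatment completion in Arm II than in Arm I. An interval-censored sensitivity analysis could be added, but it would not replace the scan near each landmark.

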 - Time to LR, a secondary outcome, will be measured as the time from the date of randomization to the date of documented occurrence of the LR. Death before occurrence of LR will be treated as a competing risk. Study subjects who are alive and free of LR at their last evaluation will be rightcensored for Time to LR on the date of their last evaluation.
- Leptomeningeal disease (LMD), a component of CNS CE, will be diagnosed by imaging results consistent with this condition (either local or diffuse leptomeningeal disease) or by examination of spinal fluid positive for malignant cells.

- Time to LMD, a secondary outcome, will be measured as the time from the date of randomization to the date of documented first occurrence of the LMD. Death before occurrence of LMD will be treated as a competing risk. Study subjects who are alive and free of LMD at their last evaluation will be right-censored for Time to LMD on the date of their last evaluation.
- Radiation Necrosis (RN) of the treated lesions. If radiation necrosis is suspected based on imaging criteria (progression of contrast-enhancing mass that is associated with reduced perfusion on dynamic MRI, increased T2 flair/T2 hyperintensive signals within previous radiation treatment fields for the index lesion), then follow-up MRI imaging (with MRS, PET/SPECT as optional) will be obtained 4-6 weeks later to confirm the diagnosis of RN. The Time to RN will be back-dated to the initial imaging-findings date if the diagnosis of RN is confirmed by the follow-up imaging.
 - Stratified by surgical site versus non-surgical sites and the use of targeted therapy, cytotoxic chemotherapy, or immunotherapy
- Symptomatic Radiation Necrosis (SRN), a component of CNS CE, will be documented radiation necrosis of the treated lesions (see above) that is accompanied by symptoms (headaches, nausea, vomiting, or other neurologic symptoms).
 - Time to SRN, a secondary outcome, will be measured as the time from the date of randomization to the date of documented occurrence of the SRN. Death before occurrence of the SRN will be treated as a competing risk. Study subjects who are alive and free of SRN at their last evaluation will be right-censored for Time to SRN on the date of their last evaluation.

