Sample-size calculations are informed by results from Patel et al.'s retrospective study.⁶ Based on their results, we expect that the post-operative SRS/SRT arm will have an average CNS CE rate of approximately 25% per year, accompanied by an average competing-risks rate of approximately 32% per year (where the competing risk is death before the CNS CE). Sample-size calculations are also informed by the fact that UAMS typically sees approximately 50 patients per year who should meet this study's eligibility requirements.

To meet its objectives, our randomized Phase II pilot study of pre-operative SRS/SRT versus post-operative SRS/SRT needs to have >80% power to detect a 50% decrease in the rate of CNS CE on the pre-operative SRS/SRT arm using a 1-sided test at 10% alpha. The power of tests under the Fine and Gray competing-risks model is well-approximated by the power of log-rank tests calculated with the competing-risk rate represented as non-zero dropout rates on each study arm. To calculate power of 1-sided log-rank tests at 10% alpha, we implement the following assumptions in PASS 16 software⁹:

- Accrual duration will be three years while minimum follow-up will be 1.5 years, leading to a total study duration of 4.5 years.
- The post-operative SRS/SRT arm will have a CNS CE rate that averages 25.0% per year.
- The pre-operative SRS/SRT arm will have a CNS CE rate that averages 12.5% per year, or half the rate on the post-operative SRS/SRT arm.
- Both arms will have a dropout rate of 32% per year due to the competing risk.
- The crossover rate from one arm to the other will be zero on both arms.
- Sample sizes will be equal on both arms.

Under these assumptions, a sample size of 52 subjects per treatment arm (a total of 104 subjects) is calculated to provide the 1-sided log-rank test (and thus the equivalent Fine and Gray test) with 80.7% power at 10% alpha to detect a 50% reduction in the CNS CE rate with pre-operative SRS/SRT relative to the CNS CE rate with post-operative SRS/SRT. Under the same assumptions, the number of CNS CE's is projected to reach expected values of 8.6 with pre-operative SRS/SRT and 17.4 with post-operative SRS/SRT for a total expected value of 26.0 by the end of the study.

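### The 18-month limit on counted MRIs conflicts with the 1.5 to 4.5 years of follow-up behind the power calculation; read per patient, it removes about 26 to 29% of expected events and about 10 points of power

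*Combined protocol and SAP*

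**What the plan says.** In Study Design and Procedures, the Follow-up paragraph has subjects "followed by Brain MRI every 2-3 months for the first year and then every 4-6 months indefinitely" once radiotherapy and surgery are complete. It ends: "MRI's will be included in study results up to 18 months". It does not say whether the limit applies to each patient or to the study, or from what date it runs.

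In Data Analysis, the sample-size section states: "Accrual duration will be three years while minimum follow-up will be 1.5 years, leading to a total study duration of 4.5 years". On that basis it gives 80.7% power with 52 subjects per arm, and projects 8.6 pre-operative and 17.4 post-operative events, "for a total expected value of 26.0 by the end of the study".

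Two other places bear on the point:

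- **Primary Objectives:** patients alive and event-free "will be right-censored for Time to CNS CE on the date of their last evaluation". No 18-month cut-off is mentioned.
- **Statistical analysis plan:** the primary outcome is to be "summarized by treatment group as CI proportions at 6, 12, and 18 months". That makes 18 months a reporting landmark. It does not say that the Fine and Gray comparison stops there.

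**The concern.** The power calculation gives each patient between 1.5 and 4.5 years of potential follow-up, 3 years on average under even accrual. A per-patient cap gives everyone at most 1.5 years. The cap reaches nearly all primary events. Local recurrence and radiation necrosis are defined on imaging, and leptomeningeal disease on imaging or "by examination of spinal fluid positive for malignant cells".

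If the Follow-up sentence is applied patient by patient, events seen on later scans, which the protocol itself schedules, would be discarded. The comparison would then lack the power stated for it, and the sample-size section requires more than 80%. The cap applies equally to both arms, so it does not bias the comparison. What is lost is information.

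The missing time origin is a smaller, related gap. The primary outcome runs from randomization, but the MRI schedule starts after treatment. By the windows in the treatment-arm table, that can be 15 + 15 = 30 days after randomization in Arm I. In Arm II ("Patients undergo surgery within 15 days of randomization followed by standard-of-care SRS or SRT within 30" days) it can be 15 + 30 = 45 days.

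**Working it through.** **Inputs (sample-size section):** 52 per arm; event rates 25.0% and 12.5% per year; competing-death rate 32% per year in both arms; 3 years of accrual; 1.5 years minimum follow-up; one-sided alpha 0.10. Even accrual is my assumption. The plan does not say whether its annual rates are hazards or proportions, so I tried all four combinations. A proportion p converts to the hazard −ln(1 − p), giving 0.2877, 0.1335 and 0.3857.

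**Formulas.** Let l be the event hazard, d the death hazard and s = l + d.

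- Events per arm, uncapped (follow-up uniform on 1.5 to 4.5 years): 52 × (l/s) × [1 − (e^(−1.5s) − e^(−4.5s)) / (3s)]
- Events per arm, capped at 1.5 years: 52 × (l/s) × (1 − e^(−1.5s))
- Schoenfeld power for D total events: Φ(√(D/4) × |ln HR| − 1.2816)

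**Worked case, all rates as hazards.**

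- Post-operative arm, s = 0.57: uncapped 52 × 0.3492 = 18.16; capped 52 × 0.2521 = 13.11.
- Pre-operative arm, s = 0.445: uncapped 52 × 0.2014 = 10.47; capped 52 × 0.1368 = 7.11.
- Totals: 28.63 uncapped and 20.22 capped, a loss of 29.4%.
- Power at HR 0.50: uncapped Φ(2.675 × 0.6931 − 1.2816) = 71.7%; capped Φ(2.248 × 0.6931 − 1.2816) = 60.9%.

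**All four readings, uncapped to capped** (HR 0.50 with event hazards, 0.464 with event proportions; Fine and Gray from 8,000 simulated trials):

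| Reading of the rates | Expected events | Loss | Schoenfeld power | Fine and Gray power |
|---|---|---|---|---|
| All hazards | 28.63 to 20.22 | 29.4% | 71.7 to 60.9% | 67.6 to 58.5% |
| All proportions | 29.01 to 21.36 | 26.4% | 78.4 to 68.9% | 73.9 to 66.0% |
| Event proportions, death hazard | 31.14 to 22.28 | 28.5% | 80.5 to 70.2% | 75.8 to 67.3% |
| Event hazards, death proportion | 26.63 to 19.38 | 27.2% | 69.4 to 59.6% | 64.5 to 58.1% |

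**The plan's own figures.** No variant tried gives 80.7% power and 26.0 events together. The third reading comes close on power (80.5%) but gives 31.1 events. With 26.0 events, Schoenfeld power is 68.6% at HR 0.50 and 75.0% at HR 0.464. That is a separate matter, so the effect of the cap is best read as a difference. Accepting 80.7% and applying the same proportional loss of events gives 70.0 to 71.3%, a drop of 9.4 to 10.7 points.

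**Sensitivity.**

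- 18 months starting 45 days after randomization: losses of 23 to 26% of events and 8 to 9 Schoenfeld points.
- Event hazards halved after year 1 (assumption): 19 to 21% of events and about 6 to 7 points.
- Event hazards down to a quarter after year 1 (assumption): 12 to 13% of events and about 4 points.

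**The case against.** The strongest reply is that the 18 months equals the 1.5-year minimum follow-up. If the sentence means 18 months after the last randomization, the sections agree and nothing is lost. That reading is possible, and no passage rules it out. But the sentence follows a schedule written for each subject and names no calendar date, so whoever abstracts the scans could reasonably apply it per patient. The text needs correcting under either reading.

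Second, the size depends on assumptions. The plan says only that the rates average 25.0% and 12.5% per year, and event hazards may well fall with time. This stands: the sensitivity results give smaller losses. Constant average rates are nevertheless the basis of the plan's own projection.

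Third, the planned test is Fine and Gray, where the loss is 6 to 9 points rather than about 10. This also stands. The figure of about 10 is the like-for-like comparison with the stated power, which is a log-rank power.

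Fourth, the capped counts should not be set against 26.0 as if the cap explained the whole gap, since that figure does not reproduce. Against 26.0 the shortfall is 14 to 25%; the effect of the cap itself is the 26 to 29% fall from the uncapped counts.

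Finally, an 18-month horizon is a legitimate choice for a pilot whose reporting landmarks stop there. If it is intended, the power statement has to match it.

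**Conclusion.** The concern holds. On its natural per-patient reading, the Follow-up sentence contradicts the sample-size section, and neither the censoring rule nor the analysis section resolves it. With constant rates, even accrual and the cap running from randomization, about 19 to 22 events remain. The cap alone removes 26 to 29% of expected events. It costs about 10 points of log-rank power or 6 to 9 points of Fine and Gray power. Under the cap, no reading of the rates reaches the required 80%, even if the stated 80.7% is taken as the starting point. Leptomeningeal disease found late by spinal fluid alone would reduce the loss slightly.

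**What to change.** Preferred: reword the Follow-up sentence so that every MRI up to a common study end date, 1.5 years after the last randomization, counts for the composite event and its components. Keep 6, 12 and 18 months as descriptive landmarks. The cost is one sentence, plus collecting and abstracting later routine scans for early enrollees, up to 4.5 years after randomization. The protocol schedules these scans but does not say where they are done, so some may have to be requested.

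If a per-patient cap is intended:

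- State administrative censoring at 18 months from randomization, in both the Primary Objectives and the Statistical analysis plan.
- Recalculate the sample-size section with follow-up capped at 1.5 years, saying whether the annual rates are hazards or proportions. Expect 19 to 22 events and about 58 to 70% power, depending on that choice and on the test. Part of this shortfall from 80.7% is already there without the cap.

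This alternative costs only a lower stated power. Either choice should be fixed before analysis, so that the data cut-off in this open-label trial is not chosen afterwards.
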